6.3.8 Oxygen Saturation

Baseline values are defined as the last measurements taken before the first dose of oliceridine. Change from baseline will be defined as the post baseline value minus the baseline value.

Potentially clinically significant abnormal (PCSA) oxygen saturation criteria is defined below:

Client: Trevena, Inc.
 Version #: 1.0
 Version Date: 20Dec2016

Protocol/CIP #: CP130-3003

Parameter	Criterion value	Change relative to baseline
Oxygen Saturation	< 90 %	NA

6.3.9 Somnolence/Sedation

The Moline-Roberts Pharmacologic Sedation Scale (MRPSS) will be used to measure somnolence/sedation. Baseline values are defined as the last measurements taken before the first dose of oliceridine. Six levels describe the range of sedation from “none to minimal” to “general anesthesia”:

Presentation	Auditory Stimulus	Tactile Stimulus	Response	Sedation
Awake, aware, alert Airway and ventilation adequate	None	None	Spontaneous, sustained interaction	1 None to Minimal
Restful, drowsy, dozing, lightly sleeping Airway and ventilation adequate	Soft voice or ambient noise	None or light touch, rubbing or tapping	Sustains interaction	2 Anxiolysis
Sleeping Airway and ventilation adequate	Soft to normal voice	Light touch, rubbing or tapping	Limited or brief interaction	3 Moderate Sedation
Sleeping Airway and ventilation adequate	Normal to loud voice	Light touch, rubbing or tapping	Follows simple commands	4 Moderate Sedation
Sleeping Airway and ventilation may be impaired	Loud voice	Intense to noxious	Purposeful response or non-purposeful	5 Deep Sedation
Sleeping Airway and ventilation likely impaired	Loud voice	Noxious	No response, unarousable	6 General Anesthesia

6.4 Drug Concentration Measurements and Pharmacokinetic Parameters

For all samples, the actual sampling time will be recorded.

6.5 Efficacy Variables

6.5.1 Numeric Pain Rating Scale (NPRS)

The NPRS is a generic, unidimensional questionnaire of pain intensity in adults. In the NPRS, a respondent selects a whole number (0-10 integers) on a single 11 point scale that best reflects the intensity of their pain. In this scale, the 0 is anchored with the descriptor “no pain” and the 10 is anchored with the descriptor “worst pain imaginable”. Baseline values are defined as the last measurements taken before the first dose of oliceridine. Change from baseline will be defined as the post baseline value minus the baseline value.

Client: Trevena, Inc.
 Version #: 1.0
 Version Date: 20Dec2016

Protocol/CIP #: CP130-3003

7. STATISTICAL METHODS

7.1 General Methodology

Data will be summarized using descriptive statistics (number of patients [N], mean, standard deviation [SD], median, minimum, and maximum) for continuous variables and using frequency and percentage for discrete variables. Unless specified otherwise, all summaries will be performed using SAS® Version 9.3 or higher.

7.2 Adjustments for Covariates

Not applicable to this study.

7.3 Handling of Dropouts or Missing Data

All dates presented in the individual patient listings will be as recorded on the eCRF, not as per the rules below. All rules explained below for partial/missing dates will be followed unless contradicted by any other data recorded on the electronic Case Report Form (eCRF).

7.3.1. Adverse Events

If the AE stop date is completely missing and the AE has resolved, the stop date will be imputed as the date of the patient's last visit in the study.

- If only the year is known, the stop date will be imputed as “31-Dec” of that year or as the date of the patient's last clinic visit in the study if in the same year.
- If the month and year are known, the stop date will be imputed as the last day of that month unless the stop date corresponds to the same month as the patient's last clinic visit in which case the date of patient's last clinic visit in the study will be used instead.

If the start date is completely missing it will be imputed as follows:

- If the stop date occurs on or after the start of study medication or the event is ongoing, the start date will be imputed as the date of the first dose of study medication.
- If the stop date occurs before the start of study medication, the start date of the event will be imputed as the patient's screening date or the stop date of the event, whichever the earlier.

If the start time is missing it will be imputed only in the case where the start date of the event corresponds to the date of the first dose of study medication. In this case the time will be imputed as the same time as the first dose of study medication. In all other cases the time will not be imputed. Imputed dates will be used for calculations, however the actual date collected will be presented in listings.

Chiltern, International – Confidential

Page 20 of 30

Chiltern, International, All rights reserved. Reproduction or transmission to others apart from the parties involved with this document in any form or by any means is not permitted without the prior written consent of Chiltern, International.

Client: Trevena, Inc.
 Version #: 1.0
 Version Date: 20Dec2016

Protocol/CIP #: CP130-3003

7.3.2. Concomitant Medications

If the stop date is completely missing and the patient has stopped taking the CM, the stop date will be imputed as the date of the patient's last visit in the study.

- If only the year is known, the stop date will be imputed as “31-Dec” of that year or as the date of the patient's last clinic visit in the study if in the same year.
- If the month and year are known, the stop date will be imputed as the last day of that month unless the stop date corresponds to the same month as the patient's last clinic visit in which case the date of patient's last clinic visit in the study will be used instead.

If the start date is completely missing it will be imputed as follows:

- If the stop date occurs on or after the start of study medication or the concomitant medication is ongoing, the start date will be imputed as the date of the first dose of study medication.
- If the stop date occurs before the start of study medication, the start date of the medication will be imputed as the patient's screening date or the stop date of the medication whichever the earlier.

If the start time is missing it will be imputed only in the case where the start date of the medication corresponds to the date of the first dose of study medication. The time will be imputed as the same time as the first dose of study medication. In all other cases the time will not be imputed. Imputed dates will be used for calculations, however the actual date collected will be presented in listings.

7.3.3. Study Medication Dosing

The start date/time of first dose of study medication is not expected to be missing for any patient in the Safety Analysis Set. If the stop date/time of last dose of study medication is completely missing, then the date/time of last dose of study medication will be assigned as the earliest of the 5 options below for analysis purposes:

1. Start date/time of last dose
2. Date/time from end of treatment phase declaration
3. Date/time of patient's first end-of-treatment phase assessment in the study
4. Early termination
5. Death (assuming time of death of 23:59 if only date is available; time may be obtained from stop time of associated AE with fatal outcome)

Client: Trevena, Inc.
 Version #: 1.0
 Version Date: 20Dec2016

Protocol/CIP #: CP130-3003

7.3.4. Medical History

If the month and year are present but the day is missing, the diagnosis date will be set to first day of the relevant month. If only the year is recorded, the diagnosis date will be set as “01-Jan” for that year. If the entire date is missing, the start date of diagnosis will remain missing.

7.3.5. Numeric Pain Rating Scale

For patients who have no NPRS assessments recorded prior to the first dose of study medication, the baseline will be imputed with a score of 4. Otherwise, there will be no imputation of missing data for NPRS.

7.3.6. Subjective Opioid Withdrawal Scale

Opioid withdrawal will be measured using the Subjective Opioid Withdrawal Scale (SOWS) consisting of 16 symptoms rated in intensity (0=Not at all, 1=A little, 2=Moderately, 3=Quite a bit, 4=Extremely). The total score will be derived by summing the individual symptom intensities and will range from 0 to 64. If there are no more than half of the symptoms that are missing from the SOWS, imputation with the mean score of the non-missing questions will be used to calculate total score. SOWS with more than half of the symptoms missing will have total score missing.

7.4 Interim Analyses and Data Monitoring

No data monitoring committees are planning for this study. An interim analysis is expected to be performed in order to support regulatory discussions. No statistical testing will be performed.

7.5 Multi-Center Studies and Pooling of Centers

This study will be conducted at approximately 60-90 study centers located in the United States. No pooling of the sites will be performed since no formal statistical tests will be performed for the different centers.

7.6 Multiple Comparisons/Multiplicity

No adjustments for multiple comparisons or multiplicity will be made.

7.7 Examination of Subgroups

The analysis of safety will be examined by looking at the following subgroups: sex (females vs. males); age grouping 1 (<65 years vs. ≥ 65 years); age grouping 2 (≥ 18 to $<$ study median years of safety analysis set population vs. \geq study median years of safety analysis set population); race (white vs non-white); median baseline NPRS score ($<$ median vs. \geq median); initial setting, BMI (<25 vs. ≥ 25), and CYP2D6 metabolizer status.

No statistical testing will be performed for the subgroup analyses but any differences in treatment effect noticed in subgroups may be explored.

Chiltern, International – Confidential

Client: Trevena, Inc.
Version #: 1.0
Version Date: 20Dec2016

Protocol/CIP #: CP130-3003

8. STATISTICAL ANALYSIS

The standard operating procedures (SOPs) of Chiltern, International, will be followed in the creation and quality control of all data displays and analyses.

8.1 Disposition of Subjects

The number of patients in each analysis set will be tabulated for all the Enrolled Analysis Set. Safety Analysis Set will be further summarized by each site and by cumulative dose group and all groups combined.

In addition, summary of reasons for screen failure will be tabulated for the Enrolled Analysis Set. The inclusion and exclusion criteria will be summarized in two separate categories. The inclusion criteria will be further categorized to patients not meeting the NPRS threshold and those not meeting other inclusion criteria. Patients with multiple reasons for failure or termination will be counted in each reason category.

Safety Analysis Set will be further summarized by cumulative dose group and all groups combined. The number of patients that completed the study, the number of patients that discontinued early, the number of patients for each reason for early discontinuation and the number of patients discontinuing at each study window will be summarized. Study window will be defined as the date and time of termination minus the date and time of first dose of oliceridine. The time point intervals are defined in section 6.2.4

Because the duration of treatment for each patient in this study will be determined by the clinical need for parenteral opioid therapy, a patient will be considered to be a completer if no early termination reason (e.g, AE to discontinuation, lack of efficacy) is indicated.

A listing with each patient's first/last dose of oliceridine, date/time of end of treatment, date of study completion and a potential reason for early termination will be provided. An additional listing with each patient's inclusion/exclusion criteria that caused the patients to be screen failures will be provided.

8.2 Protocol Deviations

Protocol deviations will be listed by patient and summarized in a table based on protocol deviation categories as collected by the Kestrel clinical trial management system. This summary will be based on the Enrolled Analysis Set. Deviation categories will include procedure window, inclusion/exclusion criteria, unapproved medication, visit window, missed procedure, informed consent, and incorrectly performed procedure. A categorization of major or minor for each deviation will be determined by Trevena and recorded in the Kestrel database, as well as included as part of the summary table.

Protocol deviations will be summarized by cumulative dose groups based on their cumulative dose received. Screening failures will not be included in this summary. The categories will be sorted by descending count of patients in the all treated patients column.

Client: Trevena, Inc.
Version #: 1.0
Version Date: 20Dec2016

Protocol/CIP #: CP130-3003

8.3 Analysis Populations

8.3.1. Enrolled Analysis Set

The enrolled population will include all patients that signed the informed consent form irrespective of whether they received oliceridine or not.

8.3.2. Safety Analysis Set

The safety analysis population will include all enrolled patients receiving at least 1 dose of oliceridine.

8.3.3. Efficacy Analysis Set

The efficacy analysis set will include all enrolled patients who received at least 1 dose of oliceridine and have at least 1 post-dose NPRS score.

8.4 Demographic and Other Baseline Characteristics

Demographic and baseline characteristics including age, height, weight, BMI, and baseline pain intensity will be summarized for each cumulative dose group and for all groups combined for the Safety Analysis Set with descriptive statistics (number of patients [n], mean, standard deviation [SD], median, minimum [min], and maximum [max]). No statistical comparisons will be performed for demographic and baseline characteristics.

Initial setting, gender, age groupings 1 and 2, race, race group, ethnicity, CYP2D6 metabolizer status, and BMI group will be summarized for each cumulative dose group and for all groups combined for the Safety Analysis Set using counts and percentages.

Data listings including demographic and baseline characteristics will be produced.

8.5 Prior and Concomitant Medications

Prior and concomitant medications will be summarized separately using the Safety Analysis Set for each cumulative dose group and for all groups combined. The World Health Organization (WHO) Drug Dictionary, version March 2016, will be used to classify medications by preferred name and WHO ATC classification of ingredients.

The number and percent of patients who took prior medications will be shown by WHO ATC classification of ingredients and by preferred term. The number and percent of patients who took concomitant medications will be shown in the same manner.

Data listings including prior and concomitant medications will be produced. Prior and concomitant medications will be distinguished directly in the listing.

8.6 Analysis of Safety

The Safety Analysis Set will be used for all safety summaries. Summaries will be tabulated by cumulative dose group and for all groups combined.

Client: Trevena, Inc.
 Version #: 1.0
 Version Date: 20Dec2016

Protocol/CIP #: CP130-3003

8.6.1. Medical History

The reasons for receiving oliceridine will be summarized by the number and percentage of patients from each initial setting, specialty, and ICD-10 category for each cumulative dose group and for all groups combined using the Safety Analysis Set.

Other medical history collected will be summarized by the number and percentage of patients from each body system and medical condition for each cumulative dose group and for all groups combined using the Safety Analysis Set. All medical history events will be coded using MedDRA version 19.0

Data listing including all medical history regardless of whether or not it was the reason for receiving oliceridine will be produced.

8.6.2. Extent of Exposure and Compliance to Study Treatment

8.6.2.1. Extent of Exposure

Each exposure summary will be summarized for each cumulative dose group and for all groups combined using the Safety Analysis Set.

The method of administration will be summarized by the number and percentage of patients using each method. Patients will have the method of administration categorized as PCA if they received at least 1 PCA dosing. Otherwise the method of administration will be categorized as bolus.

Then, regardless of the method of administration, the duration of exposure to study medication will be displayed by summary statistics (mean, standard deviation, median, minimum, and maximum). This duration will be computed as the difference in total hours from the start of the first dose of study medication to the end-time for the last dose of study medication administration.

The total amount of oliceridine administered will be computed regardless of the method of administration within the windows defined in Section 6.2.4. Subsequently, the total amount of oliceridine administered to patients over these periods will be summarized (mean, standard deviation, median, minimum, and maximum) by summary statistics.

Exposure summaries will be repeated by sex, age grouping 1, age grouping 2, race, median baseline NPRS score, BMI, CYP2D6 metabolizer status and initial setting subgroups.

Exposure data including the date, time, method of administration, dose in mg for each administration of oliceridine and the cumulative dose will be listed for each patient.

Boxplots for each cumulative dose and dose duration will be generated by site. A scatterplot will also be generated depicting all patient by duration of treatment and cumulative oliceridine dose.

Client: Trevena, Inc.
 Version #: 1.0
 Version Date: 20Dec2016

Protocol/CIP #: CP130-3003

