3.5.2 Oliceridine Dosing

3.5.2.1 General considerations

Oliceridine will be administered PRN via the IV route. Depending on the clinical considerations for which parenteral opioid therapy is warranted (eg, anticipated duration of therapy, clinical site/setting), a patient could receive oliceridine using clinician-administered bolus dosing or PCA dosing. A patient may receive both methods of administration.

As in current practice, patient need, analgesic efficacy, and adverse responses will guide oliceridine use. Consistent with current opioid prescribing practices for acute pain, oliceridine should not be administered on a fixed, around-the-clock dosing schedule.

The oliceridine dosing regimen should be initiated for each patient individually, taking into account the patient's severity of pain, patient response and prior analgesic treatment experience. Individually titrate oliceridine to a dose that provides adequate analgesia and minimizes AEs.

Trevena, Inc.

Protocol CP130-3003

Version 5.0

14 Sep 2016

Continually reevaluate patients receiving oliceridine to assess the maintenance of pain control and the relative incidence of AEs.

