6.4 Exposure Analyses

The total number of patients treated and the percentage of the overall sample treated by method of administration (bolus, PCA, both bolus and PCA) will be presented. Exposure data including date, time, and dose for each administration of oliceridine will be listed for each patient and will include the total amount of oliceridine administered using any method of administration within 0-1 hours, 1-2 hours, 2-3 hours, and every subsequent 3-hour period to 24 hours; 24-48 hours,

Trevena, Inc.

Protocol CP130-3003

Version 5.0

14 Sep 2016

and 48-72 hours, and every subsequent 24-hour period of the treatment phase. Subsequently, the amount of oliceridine administered to all patients over these periods and the total amount administered during the treatment phase will be summarized (mean, standard deviation, median, minimum, and maximum) by the method of administration (bolus, PCA, both bolus and PCA) for the safety and tolerability population. All doses of oliceridine, whether administered by IV bolus or PCA, will be listed.

Additionally, data will be presented by subgroups for descriptive purposes.

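### SAP merges patients who had both bolus and PCA into the PCA group and omits the dose-by-method summaries that Protocol 6.4 specifies, without declaring the change

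*SAP*

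**What the plan says.** Protocol 6.4 makes two commitments on method. The first is a count: the number of patients and the "percentage of the overall sample treated by method of administration (bolus, PCA, both bolus and PCA) will be presented". The second is an amount: the dose in each period and over the whole treatment phase is to be summarized "by the method of administration (bolus, PCA, both bolus and PCA) for the safety and tolerability population". The periods are "within 0-1 hours, 1-2 hours, 2-3 hours, and every subsequent 3-hour period to 24 hours", then daily. The synopsis repeats all of this. Mixed use is part of the design, since Protocol 3.5.2.1 states: "A patient may receive both methods of administration".

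SAP 6.3.1 and 8.6.2.1 give a two-level rule. One level is set by any use of the device: "Patients will have the method of administration categorized as PCA if they received at least 1 PCA dosing". The second level takes all remaining patients: "Otherwise the method of administration will be categorized as bolus". Dose and duration are then pooled. SAP 8.6.2.1 says "The total amount of oliceridine administered will be computed regardless of the method of administration within the windows defined in Section 6.2.4" and, of duration, "regardless of the method of administration, the duration of exposure to study medication will be displayed by summary statistics". Mock Table 14.3.1.1 matches the text: it has one count row for bolus and one for PCA, its columns are cumulative dose groups, and its duration and cumulative-dose rows have no split by method.

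**The concern.** The two documents describe different exposure outputs. A patient managed mainly with clinician boluses who then takes a single PCA dose is a mixed patient under the protocol and a PCA patient under the SAP. After that merger no planned summary describes PCA-only use or mixed use, and none gives dose for any method group.

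Exposure is part of the primary safety description in this single-arm study, and the two methods follow different dosing regimens (Protocol 3.5.2.2.1 and 3.5.2.2.2). The three-way split also has a declared later use: Protocol 7.7 foresees publications by method. If the SAP is followed as written, an output that the protocol specifies will not be produced, and a reader of the PCA row will not know that it includes mixed patients.

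**Working it through.** The plan states no figure to reproduce. The check is a comparison of definitions, plus a count of time periods.

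**1. Classification.** Each possible dosing history is assigned under both documents.

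| Dosing history | Protocol 6.4 | SAP 6.3.1 and 8.6.2.1 |
|---|---|---|
| Clinician bolus only | bolus | bolus |
| PCA only | PCA | PCA |
| Both | both | PCA |

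Three groups become two. Bolus-only patients are unaffected. PCA-only and mixed patients are merged.

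**2. Outputs by method.**

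| Output | Method groups in protocol | Method groups in SAP |
|---|---|---|
| Patients, n and % | 3 | 2 |
| Total dose | 3 | 0 |
| Dose per period | 3 | 0 |

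The SAP repeats its exposure summaries by sex, two age groupings, race, baseline pain, BMI, CYP2D6 status and initial setting. Method is not on that list, so the dose summaries do not come back as a subgroup table. Duration is also unsplit in the SAP, but Protocol 6.4 does not ask for duration by method, so that is not a departure.

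**3. Time periods to 24 hours.**

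- Protocol 6.4: three one-hour periods to hour 3, then three-hour periods to hour 24. That is 3 + (24 − 3)/3 = 3 + 7 = 10.
- SAP 6.2.4: 0–1, 1–4, 4–12 and 12–24 hours, which is 4.

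The SAP windows are not simple groupings of the protocol periods, because the cut at 4 hours falls inside the protocol's 3–6 hour period. After 24 hours the picture is mixed. The SAP is finer for 24–48 hours (two 12-hour windows), agrees for 48–72 and 72–96 hours, and has one open window from 96 hours where the protocol continues by day.

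**4. The table shell.** Mock Table 14.3.1.1 shows how many patients were exposed in each window and the overall cumulative dose. It has no row for dose per window, so even the SAP's own pooled per-window summary lacks a place in the shell.

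**5. Was the change declared?** Protocol section 6 requires any change from its analyses to be described in the SAP and in the study report. SAP section 5 lists no change and refers the reader to the protocol amendments. Protocol version 5.0 still carries the three-way text.

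**The case against.** The strongest reply is that little is lost. SAP 8.6.2.1 and Listing 16.2.3.1 keep the method, time and amount of every administration, so the three groups and the protocol's periods can be rebuilt at any time. The study is descriptive and has no hypothesis tests. The any-PCA rule is explicit, so patients are classified as the SAP intends. The protocol itself adds up dose over any method within a patient, so pooling at patient level is not a departure. All of this stands, and it limits the point to missing summaries and a loose label.

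Two stronger readings are tempting, and the documents support neither. A reader might infer that the PCA group's mean dose will be inflated by bolus doses. No planned table gives a dose in mg for either method, so there is no such mean to bias. A reader might also infer that adverse events by method have been dropped. Protocol 6.3 asks for adverse events overall and by severity and causality, not by method.

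A further fair objection is that the protocol's own groups are not fully defined. The PCA regimen in Protocol 3.5.2.2.2 includes a loading dose and allows supplemental doses, and neither document says whether these count as bolus. If they do, nearly every PCA patient could be classed as mixed. This is a reason to write the rule down. It does not justify dropping the category without saying so.

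**Conclusion.** The discrepancy is real and undeclared. Under the SAP as written, method groups fall from three to two for patient counts and from three to none for dose, and time resolution over the first 24 hours falls from 10 periods to 4. Every patient who has both methods is labelled PCA. That follows from the rule itself and says nothing about how many such patients there will be; the documents give no expected number, so no effect in patients or in mg can be calculated.

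This is a shortfall in planned reporting, not a loss of data or a biased estimate. It should be corrected because the protocol commits to the output and the data for it are already collected. The conclusion assumes that version 5.0 is the governing protocol text. SAP section 5 refers to an approved amendment 5; if that is a later document, it should be checked for a change to section 6.4.

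**What to change.** - In SAP 6.3.1, SAP 8.6.2.1 and mock Table 14.3.1.1, use three mutually exclusive groups: bolus only, PCA only, and both.
- State, for classification only, whether the PCA loading dose and the supplemental doses given during PCA count as part of PCA or as bolus, so that the mixed group does not absorb nearly all PCA patients.
- Add total dose, and dose in each Protocol 6.4 period, by those three groups (mean, SD, median, minimum and maximum).
- Describe and justify in SAP section 5 any departure that the sponsor prefers to keep, including the coarser windows, and carry it into the study report.

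A summary of treatment-emergent adverse events by method would be a reasonable optional addition, but it is not a protocol commitment.

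The cost is one classification rule and a few extra table rows or columns. No new data are needed.
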